4.2. Efficacy Endpoints

4.2.1. Secondary Endpoints

4.2.1.1. Best Overall Response

BOR will be determined using time point responses (TPRs) up until the last evaluable TPR prior to or on the date of (i) disease progression as defined by RECIST Version 1.1 (Eisenhauer et al., 2009) or RANO criteria for glioma patients, or death; or (ii) withdrawal of consent or lost to follow-up; or (iii) receiving subsequent anti-cancer medications, whichever is earlier.

The timing of an overall TPR will always be derived based on scan dates, not response assessment dates. For a scheduled tumor scan assessment, it is expected that there may be a variation for the actual timing of scans among target, non-target, and new lesions. In assigning a date for the overall response assessment at a visit, the earliest date collected at that visit will be used. Within a grouped timepoint, if there are multiple assessments on different dates for the same target lesions, the last assessment will be used.

BOR as defined by RECIST:

A patient's BOR will be determined based on [Table 2](#).

There are two ways of assigning BOR for a patient when the minimum interval for confirmation of CR and PR is not satisfied or if there are no confirmatory scans for CR and PR:

- Adding two more response categories as: unconfirmed CR, unconfirmed PR;
- Assigning BOR as SD, that is, both the unconfirmed CR and unconfirmed PR will be SD.

Both ways of assigning BOR will be implemented.

The number and percentage of patients in each category of derived BOR (Confirmed CR, Confirmed PR, SD, PD, or NE) will be summarized.

Table 2 Best Overall Response When Confirmation of CR and PR are Required

First TPR	Second TPR	Best overall response*^ for ORR	Best Overall Response for ORR _{UNCONFIRMED}
CR	CR	CR	CR
CR	PR	SD [b] or PD	Unconfirmed CR
CR	SD	SD [b] or PD	Unconfirmed CR
CR	PD	SD [b] or PD	Unconfirmed CR
CR	NE or NA	SD [c] or NE or NA	Unconfirmed CR
PR	CR	PR	Unconfirmed CR
PR	PR	PR	PR
PR	SD	SD [d]	Unconfirmed PR
PR	PD	SD [b] or PD	Unconfirmed PR
PR	NE or NA	SD [c] or NE or NA	Unconfirmed PR
NE	NE	NE	NE
NE	CR	SD	Unconfirmed CR
NE	PR	SD	Unconfirmed PR

NE	SD	SD	SD
NE or NA	PD	PD	PD
SD	PD	SD [b] or PD	SD [b] or PD
SD	CR	SD	SD
SD	PR	SD	SD
SD	SD	SD	SD
SD	NE or NA	SD [c] or NE or NA	SD [c] or NE
PD	No further evaluation	PD	PD

CR = Complete Response; NE = Not Evaluable; NA = Not Available; ORR = Objective Response Rate; PD = Progressive Disease; PR = Partial Response; SD = Stable Disease.

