4.2.1.2. Objective Response Rate, and Disease Control Rate

Objective response rate (ORR) by RECIST will be calculated using two different ways:

- Scenario #1: ORR will be calculated using a strict interpretation of RECIST Version 1.1. Objective response will be derived as no/yes variable. Patients with a BOR of confirmed CR or PR will be assigned ‘Yes’. Patients not having a BOR of confirmed CR or PR will be assigned ‘No’. Hence, ORR is defined as the proportion of patients with confirmed objective response being “Yes”.
- Scenario #2: ORR_{UNCONFIRMED} will be calculated using all responses regardless of confirmation. Objective response will be derived as no/yes variable. Patients with a BOR of confirmed CR, confirmed PR, unconfirmed CR or unconfirmed PR will be assigned “Yes”. All patients with other BOR values will be assigned “No”. Hence, ORR_{UNCONFIRMED} is defined as the proportion of patients with unconfirmed objective response being “Yes”.

Both ways (confirmed and unconfirmed) of assigning BOR will be implemented.

ORR defined as the proportion of patients with a confirmed BOR of complete response (CR) or partial response (PR) as determined by the investigator using RECIST v1.1.

ORR by RANO is defined as the proportion of patients with a BOR of complete response (CR) or partial response (PR) or MR as determined by the investigator using RANO.

Disease control rate (DCR) by RECIST is defined as the proportion of patients with a BOR of CR, PR, or SD lasting at least 7 weeks as determined by the investigator using RECIST v1.1.

DCR by RANO is defined as the proportion of patients with a BOR of CR, PR, MR, or SD lasting at least 7 weeks as determined by the investigator using RANO criteria for glioma patients.

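### The unconfirmed-response column of SAP Table 2 codes SD followed by CR or PR as SD, against the SAP's own definition of ORR regardless of confirmation

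*SAP*

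**What the plan says.** SAP section 4.2.1.1 gives two ways to assign a RECIST BOR "when the minimum interval for confirmation of CR and PR is not satisfied or if there are no confirmatory scans for CR and PR". The first is "Adding two more response categories as: unconfirmed CR, unconfirmed PR". Under the second, "both the unconfirmed CR and unconfirmed PR will be SD". The SAP will carry out both. Table 2, titled "Best Overall Response When Confirmation of CR and PR are Required", does so in two result columns, one for confirmed ORR and one for ORR regardless of confirmation.

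Section 4.2.1.2, Scenario #2, says the latter rate "will be calculated using all responses regardless of confirmation". A BOR of confirmed or unconfirmed CR or PR makes the patient a responder; any other BOR makes the patient a non-responder.

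In the last column of Table 2, two rows that start with an unevaluable scan read "NE CR SD Unconfirmed CR" and "NE PR SD Unconfirmed PR" (first response, second response, confirmed column, unconfirmed column). The two rows that start with SD and move to CR or PR show SD in both result columns. No footnote to Table 2 exempts these two rows, and SAP section 7 does not list them as a deliberate change.

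**The concern.** The last column exists to apply the first way of assigning BOR. For SD–CR and SD–PR it instead shows the result of the second way, identical to the confirmed column. A patient with SD at week 8, PR at week 16 and no later scan would count as a non-responder. A patient whose week 8 scan was unreadable, with the same PR at week 16, would count as a responder. Neither has a confirmatory scan.

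At stake is the responder status of individual patients in a rate that SAP section 5.2.9.1 reports with Clopper-Pearson intervals by dose and disease cohort. If the text and the table give different answers, the programmer chooses between them, possibly after the data have been seen.

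**Working it through.** **Step 1: table against definition.** The responder rule of section 4.2.1.2 was applied to the last column of every Table 2 row containing a CR or PR. There are 5 rows starting with CR, 5 starting with PR, 2 with NE then CR or PR, and 2 with SD then CR or PR: 5 + 5 + 2 + 2 = 14. The instructive rows are:

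| First | Second | Confirmed column | Unconfirmed column | Responder by table | Responder by 4.2.1.2 |
|---|---|---|---|---|---|
| NE | CR | SD | Unconfirmed CR | Yes | Yes |
| NE | PR | SD | Unconfirmed PR | Yes | Yes |
| PR | PD | SD or PD | Unconfirmed PR | Yes | Yes |
| SD | CR | SD | SD | **No** | Yes |
| SD | PR | SD | SD | **No** | Yes |

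The other rows agree, so 14 − 2 = 12 follow the definition. SD in the confirmed column is not in question.

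**Step 2: longer sequences.** Table 2 has two time-point responses (TPRs) per row. Apart from its footnote on one intervening NE or SD, the SAP does not say how to apply it to three or more. To see what turns on this, take every sequence of k TPRs in which PD can only be last. There are 4^(k−1) × 5 sequences, of which 2^(k−1) × 3 contain no CR or PR. Sequences with a response number 20 − 6 = 14 for k = 2, 80 − 12 = 68 for k = 3, and 320 − 24 = 296 for k = 4. Those the table misses are:

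| Reading | k = 2 | k = 3 | k = 4 |
|---|---|---|---|
| (a) First two TPRs only | 2 of 14 | 18 of 68 | 96 of 296 |
| (b) Every adjacent pair | 2 of 14 | 4 of 68 | 8 of 296 |
| (c) Adjacent pairs, with NA added after the last scan | 0 | 0 | 0 |

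- Reading (a), k = 3: SD–CR or SD–PR followed by any of 5 outcomes gives 10. Two uninformative TPRs (4 pairs of SD or NE) followed by CR or PR gives 8. The total is 18. For k = 4 the same split is 2 × 20 = 40 plus 4 × 14 = 56, total 96. Only the first part of each sum comes from the two cells; the rest comes from ignoring later scans.
- Reading (b): the missed sequences have no earlier response, SD next to last, and CR or PR last. Their number is 2^(k−2) × 2 = 2, 4, 8.
- Reading (c): the row for PR followed by NE or NA rescues the patient, but the same patient is then SD by one row and Unconfirmed PR by another.

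These are counts of possible sequences, not probabilities for patients.

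**Step 3: size.** One reclassified patient in a group of n moves the rate by 1/n. The SAP does not give the number of response-evaluable RECIST patients per group, so n is assumed: 1/3 = 33.3 points, 1/6 = 16.7 points, 1/10 = 10.0 points. For n = 6 with one responder already counted, 1/6 = 16.7% (95% Clopper-Pearson interval 0.4 to 64.1) becomes 2/6 = 33.3% (4.3 to 77.7).

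**The case against.** The strongest reply is that little depends on these cells. The primary endpoints of Part 1 are safety and MTD/RP2D (SAP section 2.1). Protocol section 9.2.7 defines ORR on confirmed response, and the unconfirmed rate is a supplementary SAP addition. No hypothesis is tested. RECIST DoR and TTR use confirmed responders only, PFS does not use BOR, DCR counts these patients either way, and glioma patients follow a separate RANO algorithm. All of this stands, and it limits severity.

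The reply continues that the text already shows the intent, so the cells look like a carry-over from the confirmed column. That is plausible, but the table is what gets programmed, and it still gives the other answer.

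A reader might infer that late responders are dropped in general. The documents do not support that. Read by adjacent pairs, SD–PR–PR gives PR, while SD–PR–SD and SD–PR–PD give Unconfirmed PR. The loss is then confined to a response at the last TPR directly after SD. That pattern is narrow but realistic: with scans every 8 weeks to week 24, a first PR at week 16 needs only withdrawal, new therapy or data cut-off before the next scan.

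A reader might also infer that the row for PR followed by NE or NA openly contradicts the SD–PR row. It has PR as the first TPR, so the conflict arises only under reading (c), which the SAP does not state.

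**Conclusion.** The inconsistency is real and visible in the SAP: two cells contradict Scenario #2, the first way of assigning BOR, and the parallel NE rows. It changes only the RECIST ORR regardless of confirmation and the unconfirmed BOR categories behind it. Who is affected depends on an unstated reading. By adjacent pairs, it is a patient whose only CR or PR is the last TPR directly after SD; by the first two TPRs only, it is more patients. The number of such patients is unknown, and the 16.7 points rests on an assumed group of 6. The planned 27 to 36 subjects do not give a usable denominator: they include gliomas, and efficacy is reported by dose level and disease type, with no pooled RECIST group stated.

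A reader might infer that the trial's efficacy conclusions are at risk. They are not, since the protocol-defined ORR is unchanged. Severity is minor to moderate.

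**What to change.** In the last column of Table 2 only, change SD–CR to Unconfirmed CR and SD–PR to Unconfirmed PR. All 14 rows then agree with section 4.2.1.2.

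Add one sentence for sequences of more than two TPRs: any CR or PR inside the BOR window of section 4.2.1.1 that is not confirmed counts as Unconfirmed CR or Unconfirmed PR in this column. The sentence is needed because the two cells alone do not settle reading (a), where 8 of the 18 missed three-TPR sequences would remain. Leave the 49-day SD rules and the confirmed column as they are.

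A looser rule, such as the best single response before progression or new therapy, should be avoided. It would override the 49-day rule in the SD–PD row of the same column, blur confirmed and unconfirmed categories, and omit the cut-off at withdrawal or loss to follow-up.

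The cost is two cells, one sentence and a programming check, with no new data. It belongs before database lock; if made later, it should be recorded in the study report, as SAP section 1 requires for deviations.

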APPENDIX 9 RESPONSE ASSESSMENT IN NEURO-ONCOLOGY CRITERIA FOR GLIOMAS

Patients should be assessed with the same imaging method throughout the trial, with pre-specified imaging parameters.

General minimum imaging protocol of low-grade glioma:

Basic Magnetic Resonance Imaging Protocol (All Centers)

- Axial fluid-attenuated inversion recovery (FLAIR) (canthomeatal alignment): 3- to 5-mm sections, 1-mm interslice gaps, slice registration preserved as much as possible between sequential studies
- Axial T2: 5-mm sections, 1-mm interslice gap
- Coronal T1: 5-mm sections, 1-mm interslice gap
- Post-gadolinium chelate (contrast agent as per local clinical practice): coronal T1 and axial T1

(Alternatively, pre-gadolinium and post-gadolinium volumetric T1 may replace axial and coronal T1-weighted sequences)

Response	Criteria
Complete response	Complete response requires all the following criteria compared with the baseline scan: 
 • complete disappearance of the lesion on T2 or FLAIR imaging (if enhancement had been present, it must have resolved completely) • no new lesions, no new T2 or FLAIR abnormalities apart from those consistent with radiation effects, and no new or increased enhancement • patients must be off corticosteroids or only on physiological replacement doses • patients should be stable or improved clinically.
Partial response	Partial response requires all of the following criteria compared with the baseline scan: 
 • greater than or equal to 50% decrease in the product of perpendicular diameters of the lesion on T2 or FLAIR imaging sustained for at least 4 weeks compared with baseline • no new lesions, no new T2 or FLAIR abnormalities apart from those consistent with radiation effects, and no new or increased enhancement • patients should be on a corticosteroid dose that should not be greater than the dose at time of baseline scan, and should be stable or improved clinically.

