Minor response	Minor response requires the following criteria compared with baseline: 
 • a decrease of the area of non-enhancing lesion on T2 or FLAIR MR imaging between 25% and 50% compared with baseline • no new lesions, no new T2 or FLAIR abnormalities apart from those consistent with radiation effect, and no new or increased enhancement • patients should be on a corticosteroid dose that should not be greater than the dose at time of baseline scan, and should be stable or improved clinically.
Stable disease	Stable disease is present if the changes do not qualify for complete, partial, or minor response or progression and requires: 
 • stable area of non-enhancing abnormalities on T2 or FLAIR imaging • no new lesions, no new T2 or FLAIR abnormalities apart from those consistent with radiation effect, and no new or increased enhancement

Response	Criteria
	
 patients should be on a corticosteroid dose that should not be greater than the dose at time of baseline scan, and should be stable or improved clinically.
Progressive disease (≥12 weeks after radiation therapy completion)	
Progression is defined by any of the following:
 
 development of new lesions or increase of enhancement (radiological evidence of malignant transformation) a 25% increase of the T2 or FLAIR non-enhancing lesion on stable or increasing doses of corticosteroids compared with baseline scan or best response after initiation of therapy, not attributable to radiation effect or to comorbid events definite clinical deterioration not attributable to other causes apart from the tumour, or decrease in corticosteroid dose failure to return for evaluation because of death or deteriorating condition, unless caused by documented non-related disorders.

FLAIR = fluid-attenuated inversion recovery; MR = magnetic resonance.

Source: Response assessment in neuro-oncology (a report of the RANO group): assessment of outcome in trials of diff use low-grade gliomas. Lancet Oncol. 2011;12:583-93 [[van den Bent et al 2011](#)].

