[a]The minimum interval for confirmation of CR and PR is 4 weeks.

[b]Best response will be SD if the first time point overall response is after 49 days on study. Otherwise, the best response will be PD.

[c]Best response will be SD if the first time point overall response if after 49 days on study. Otherwise, the best response will be NE.

[d]Best response will be SD provided the criteria for PD have not been met from the first to second assessment.

* A best overall response of SD can only be made after the patient is on study for a minimum of 49 days (counted from Cycle 1 Day 1). If the patient is on study for less than 49 days, any tumor assessment indicating stable disease before this time period will have a best response of NE unless PD is identified.

^ Subsequent documentation of a CR may provide confirmation of a previously identified CR even with an intervening NE (e.g., CR NE CR). Subsequent documentation of a PR may provide confirmation of a previously identified PR even with an intervening NE or SD (e.g., PR NE PR or PR SD PR). However, only one (1) intervening NE or SD will be allowed between CRs or PRs for confirmation. Note: in the following scenario, PR SD NE PR, the second PR is not a confirmation of the first PR.

BOR as defined by RANO (for glioma patients):

The BOR was the best response among all the available time point responses (TPRs), the category of TPRs includes CR, PR, MR, SD, PD, and NE, and the order of the response is CR>PR>MR>SD>PD>NE. The hierarchical algorithm of deriving BOR category is detailed below.

- CR = at least one determination of CR. For example, a patient with 3 TPRs being CR, MR, and SD, then the BOR for this patient is CR.
- PR = at least two consecutive determinations of PR at least 4 weeks apart and before first documented PD or PR being the first response and being sustained for at least 4 weeks. For the consecutive determination of PR, the subsequent documentation of a PR may provide confirmation of a previously identified PR even with an intervening NE, SD, or MR (e.g., PR NE PR, PR SD PR, or PR MR PR). However, only one (1) intervening NE, SD, or MR will be allowed between PRs for confirmation, that is, in the following scenario, PR SD NE PR, the second PR is not a confirmation of the first PR. For PR being the first response, one intervening NE can be allowed before the response of PR, that is, in the response sequence of NE PR, the PR can also be considered as the first reported response.

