For example, (i) consecutive determinations of PR: a patient with 3 TPRs being PR, PR, and SD, and the duration between the two PRs is 6 weeks, then the BOR for this patient is PR; (ii) PR being the first response: a patient with 3 TPRs being PR, MR, and SD, and the duration between first dose date and the PR is 5 weeks, then the BOR for this patient is PR; a patient

with 2 TPRs being SD, PR, then the PR will be downgraded to MR, hence, the BOR will be MR.

- MR = at least one determination of MR or not qualifying for PR criteria given that there are TPRs being PR. For example, (i) a patient with 3 TPRs being MR, SD, and SD, then the BOR for this patient is MR; (ii) a patient with 2 TPRs being SD and PR, however, the PR did not meet the criteria for BOR being PR, then the PR will be downgraded to MR, hence, the BOR for this patient will be MR.
- SD = at least one SD assessment or better before first documented PD (and not qualifying for CR, PR, MR, and PD). For example, a patient with 3 TPRs being SD, NE, and PD, then the BOR for this patient is SD.
- PD = PD after the first dose date and not qualifying for CR, PR, MR, and SD.
- NE = all other cases but patients are evaluable

The number and percentage of patients in each category of derived BOR (CR, PR, MR, SD, PD, or NE) will be summarized.

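### The SAP's RANO rule lets an intervening SD or MR stand between two PRs as confirmation, which conflicts with the sustained-decrease and progression criteria in Protocol Appendix 9

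*SAP*

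**What the plan says.** SAP 4.2.1.1 derives best overall response (BOR) for gliomas from investigator time point responses, using data "up until the last evaluable TPR prior to or on the date of (i) disease progression", death, withdrawal, loss to follow-up or new therapy.

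- **PR, two-visit route.** Two PRs at least 4 weeks apart are needed, and the second may confirm the first "even with an intervening NE, SD, or MR (e.g., PR NE PR, PR SD PR, or PR MR PR". Only one such visit is allowed.
- **PR, first-response route.** The alternative is worded "before first documented PD or PR being the first response and being sustained for at least 4 weeks". The worked example is "a patient with 3 TPRs being PR, MR, and SD, and the duration between first dose date and the PR is 5 weeks", which gives BOR = PR with no second PR.
- **A PR that meets neither route** is downgraded to MR.
- **CR.** One determination is enough: "a patient with 3 TPRs being CR, MR, and SD, then the BOR for this patient is CR".

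Under SAP 4.2.1.2, RANO ORR counts CR, PR and MR. Under SAP 4.2.1.3, the RANO duration-of-response (DoR) analysis includes only patients with CR or PR.

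Protocol Appendix 9 asks for a PR with at least a 50% "decrease in the product of perpendicular diameters of the lesion on T2 or FLAIR imaging sustained for at least 4 weeks compared with baseline". MR is an area decrease of 25% to 50%. SD is the remainder, provided progression is not met. PD includes a 25% increase "compared with baseline scan or best response after initiation of therapy", on stable or increasing corticosteroids and not due to radiation effect or comorbid events.

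**The concern.** The intervening-visit allowance closely follows the RECIST confirmation footnote under SAP Table 2. In RECIST, PR and SD adjoin, so a small change can move a patient from PR to SD without progression. In Appendix 9 the whole MR band lies between PR and SD, and progression is measured against best response. A patient who goes from PR to SD has therefore normally progressed, and one who goes from PR to MR may have.

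For the PR-to-SD row, SAP Table 2 has a guard: footnote [d] accepts SD only if PD criteria were not met between the two assessments. The RANO text has no equivalent. At stake are the depth of response credited to a patient, who enters the DoR analysis, and, if a visit is mislabelled, the date of a PFS or DoR event.

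**Working it through.** The plan states no figure on this point, so there is nothing to reproduce. The check is threshold arithmetic on Appendix 9, with lesion area as a fraction of baseline.

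**Inputs (Appendix 9).** CR = 0; PR ≤ 0.50; MR 0.50 to 0.75; SD > 0.75 and not PD; PD ≥ 1.25 × the smaller of baseline and best area. Appendix 9 does not say whether the 25% is in area or diameter. I use area, because PR and MR are defined on area or diameter product, and give the diameter reading as the range.

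**1. PR to SD, area reading.** The smallest possible rise is 0.75/0.50 = 1.50, so the rise exceeds 50% against a limit of 25%. From a PR at 0.40 it is 0.75/0.40 = 1.875, or 87.5%. The limit is always exceeded, and only the Appendix 9 qualifiers can leave the visit as SD.

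**2. PR to SD, diameter reading.** If both diameters grow 25%, area grows by 1.25² = 1.5625. After a PR at 0.50 the limit is 0.50 × 1.5625 = 0.781, so an SD between 0.75 and 0.781 is not PD. SD is always PD only when the PR area is ≤ 0.75/1.5625 = 0.48.

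**3. PR to MR, area reading.**

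| Best (PR) area | PD limit = 1.25 × best | Share of MR band that is PD = (0.75 − limit)/0.25 |
|---|---|---|
| 0.50 | 0.625 | 50% |
| 0.45 | 0.5625 | 75% |
| 0.40 or less | 0.50 or less | 100% |

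**4. Sustained decrease.** An MR or SD scan is by definition one without a 50% decrease. If it falls between two PRs, the decrease was not sustained from one to the other, whether or not the scan is PD. Only an NE leaves the question open.

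**5. Why the rule works in RECIST.** Appendix 8 sets PR at ≤ 0.70 of the baseline sum and PD at 1.20 × nadir (plus 5 mm). From 0.70 the limit is 0.70 × 1.20 = 0.84, so an SD between 0.70 and 0.84 is not PD. The RANO counterpart is 0.50 × 1.25 = 0.625, which is below the start of the SD band at 0.75.

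**6. Effect on derived endpoints.** The scans shown as SD or MR are taken as labelled, and a first PR is taken at least 4 weeks after first dose.

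| Sequence | BOR now | BOR with NE only | RANO ORR | RANO DoR |
|---|---|---|---|---|
| PR-SD-PR | PR | PR (first-response route) | unchanged | unchanged |
| SD-PR-SD-PR | PR | MR | unchanged | in now, then out |
| SD-PR-MR-PR | PR | MR | unchanged | in now, then out |
| SD-PR-PD-PR | MR (window closes at PD) | MR | unchanged | out |
| CR-MR-SD | CR | CR | unchanged | in |

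**7. PFS and DoR, only if a PD visit is recorded as SD.** Take scans at weeks 8, 16 and 24 (days 57, 113 and 169) read PR, SD, PR, where the week 16 scan meets PD.

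- PFS should be an event at 113/30.4375 = 3.7 months. The patient is instead event-free to at least 169/30.4375 = 5.6 months.
- DoR should be (113 − 57 + 1)/30.4375 = 1.9 months. It becomes at least (169 − 57 + 1)/30.4375 = 3.7 months.
- The shift is at least 169 − 113 = 56 days, or 1.8 months.

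**The case against.** A reader might infer that the SAP scores glioma progressions as confirmed responses. The documents do not support that. BOR stops at RANO progression, the two PRs must precede documented PD, and Appendix 9 SD excludes anything that qualifies as progression. A visit recorded as PD gives PR-PD-PR, and the second PR is never used.

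A reader might also infer that the clause itself biases PFS and DoR dates. It does not: event dates follow documented PD, and deleting the words moves no date. The shift in step 7 needs a mislabelled visit. Nor does CR-MR-SD give a wrong BOR. One CR suffices, Appendix 9 sets no confirmation interval for CR, and the CR precedes whatever the MR visit turns out to be.

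Three further points stand. PR-MR-PR is not always a progression. Growth after a corticosteroid reduction, or from radiation or comorbid events, can leave a valid SD after PR. And PR-SD-PR with PR as the first response already earns PR by the other route.

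Two things survive. The clause still conflicts with the sustained-decrease requirement for both SD and MR. And a mislabelled visit has no safeguard: response is investigator-assessed (Protocol 6.1.13), the documents describe image storage and processing but no central response read, and the SAP has no check on areas. RANO worked examples that run from PR or CR down to SD without mention of PD make scoring against baseline alone easier to overlook.

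**Conclusion.** The conflict is real but limited. SAP 4.2.1.1 accepts confirmation sequences that fail the sustained decrease in Appendix 9. On the area reading, PR to SD always exceeds the PD limit, qualifiers aside; on the diameter reading this is certain only for a PR area of 0.48 or less. PR to MR is PD in part.

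The direct error arises where PR is not the first response: BOR is PR instead of MR, and the patient enters the RANO DoR analysis. RANO ORR does not move. Upward bias in PFS and DoR is conditional on a PD-qualifying visit being recorded as SD or MR. After CR, the MR visit should be checked for a PD event, although BOR stays CR.

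Severity is moderate: these are secondary, descriptive endpoints with no hypothesis test, in an escalation part of about 27 to 36 subjects across tumor types. The number of gliomas is not given, so no expected count of affected patients can be stated.

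Assumptions: the first-response route is taken as the SAP applies it, counting the 4 weeks from first dose; DoR entry follows the sentence restricting it to CR or PR; and Appendix 9 is unchanged. The SAP cites Protocol Amendment 3, while the protocol reviewed is Amendment 2.

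**What to change.** 1. In SAP 4.2.1.1 (RANO), allow at most one intervening NE between two PRs for confirmation, and delete SD and MR with their examples.
2. Keep BOR = CR in the CR-MR-SD example, but note that the MR visit must be checked for PD, or use another example.
3. State that the 25% increase is in area.
4. Before database lock, list recorded T2/FLAIR areas against the best area and query the investigator on any SD after PR, any MR or SD after CR, and any MR with area ≥ 1.25 × best. PD status for BOR, DoR and PFS then follows the investigator's resolved assessment under Appendix 9, including its qualifiers. The program should not override it.
5. Confirm that Appendix 9 is the same in Amendment 3.

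The cost is a few lines of SAP text and one data listing. This assumes that lesion measurements are in the database, which the planned waterfall and spider plots already require. The downside is that a few gliomas may move from PR to MR and leave the DoR analysis, or have an earlier PFS or DoR event.
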